#### 4.1.3 Additional Efficacy Parameters of Interest

- Pain score using 11-point NRS from baseline (highest pain score within the past 7 days of Day 1) to Week 26 (highest pain score during the past 7 days of Week 26)
- Percentage of patients with normalized CRP levels at 8 weeks (for patients with CRP  $\geq 1.0$  mg/dL at baseline)
- Percentage of patients with pericarditis recurrence during the EP
- Percentage of patients with normalized CRP levels at 26 weeks (for patients with CRP  $\geq 1.0$  mg/dL at baseline)
- Time to CRP normalization for patients with CRP  $\geq 1.0$  mg/dL at baseline
- CRP change from baseline at 26 weeks (%)

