7 STAGED STATISTICAL ANALYSIS (SSA)

As mentioned in section 1, the analyses for this trial will be done in a staged manner – i.e. the first analysis will be performed for data collected up to the week 8 visit and the second analysis will be done when the last patient last visit is performed and the database is declared ready for complete database lock. The following data will be presented in the SSA:

- Baseline data for all patients enrolled:
 - Patient demographics: age, gender, race, ethnicity
 - Past medical history: N (%) of patients by previous episodes of pericarditis category (i.e., 2, 3, 4, or >4);
 - N (%) of patients for whom medications at baseline were prescribed for pain and pericarditis: analgesics, opiates, NSAIDs, colchicine and corticosteroids. The medications concerned will be identified as those with following

Anatomical Therapeutic Chemical (ATC) classification: H02 (Corticosteroids for systemic use), M01 (anti-inflammatory and antirheumatic products), M04 (antigout preparations), N02A (Opioids), N02B (other analgesics and antipyretics)

- N (%) of patients prescribed medications for pain and pericarditis i.e. medications which were started up to and including the Week 8 visit date and for which the stop date was either empty or > enrolment date at the time of enrolment
- CRP value at baseline will be summarized as a continuous variable
- NRS scores at baseline will be summarized as a continuous variable
- Primary efficacy endpoint, i.e. the change in patient-reported pericarditis pain using an 11-point NRS from baseline to 8 weeks – see section 8.5.1.
- Additional efficacy endpoints (see section 8.5.2):
 - Patients with normalized CRP levels (i.e. with a CRP \leq 0.5 mg/dL) at 8 weeks (for patients with CRP \geq 1.0 mg/dL at baseline) will be summarized as a categorical variable.
 - Time to CRP normalization (in days – see section 8.5.2) up to the Week 8 visit date for patients with CRP \geq 1.0 mg/dL at baseline will be summarized as a continuous variable. If CRP had not normalized at the timepoint assessed in the analysis (e.g. week 8), the patients concerned was not included in the analysis - Time to CRP normalization
 - CRP change from baseline at 8 weeks will be summarized as a continuous variable.
- Study drug exposure:
 - N (%) of patients with highest tolerated dose of (up to Week 8 visit date):
 - 10mg/kg of body weight b.i.d.
 - 7.5mg/kg of body weight b.i.d.
 - 5.0mg/kg of body weight b.i.d.

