8.3.2 Pericarditis History

Variable label:	Comment / category labels:
Days since current pericarditis episode was diagnosed prior to IMP start	Take as date of first study treatment dose – date current pericarditis diagnosed. Tabulate as continuous variable.
Symptoms present at time of diagnosis 
 • Pericarditic chest pain • Pericardial rub • New widespread ST-segment elevation or PR segment depression according to ECG findings • Pericardial effusion (new or worsening) 	Tabulate as number of patients with the symptom ticked
CRP level ≥ 1.0 mg/dL within prior 7 days of screening?	Tabulate as categorical variable = Yes./No
Confirmation of Pericarditis diagnosis	Tabulate as categorical variable = CRP level ≥ 1.0 mg/dL within prior 7 days and Pericarditis confirmed by CMR or CRP level ≥ 1.0 mg/dL within prior 7 days only or Pericarditis confirmed by CMR only (CRP < 1.0 mg/dL) Source: reply to inclusion criteria 4.a and 4.b as 'Yes'
Number of previous episodes of pericarditis	Tabulate as categorical variable = 2 episodes,3 episodes,4 episodes or >4 episodes.

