8.5.2 Additional efficacy analysis

- The change in patient-reported pericarditis pain using an 11-point NRS from baseline to 26 weeks will be summarized as a continuous variable.
- The change in patient-reported pericarditis pain using an 11-point NRS from baseline to other intermediate weeks (i.e. visits 3,4,5,6,7) will be summarized as a continuous variable.
- Patients with normalized CRP levels (i.e with a CRP \leq 0.5 mg/dL) at 8 weeks (for patients with CRP \geq 1.0 mg/dL at baseline) will be summarized as a categorical variable
- Patients with normalized CRP levels (i.e with a CRP \leq 0.5 mg/dL) at 26 weeks (for patients with CRP \geq 1.0 mg/dL at baseline) will be summarized as a categorical variable
- Patients with pericarditis recurrence during the extension period (EP), i.e with an adverse event occurring between week 8 and week 26 and coded with the following LLT code 10087207 (Recurrent pericarditis) will be summarized as a categorical variable

- Time to CRP normalization (in days) (i.e time between IMP start date up to the first blood draw date when $CRP \leq 0.5 \text{ mg/dL}$) for patients with $CRP \geq 1.0 \text{ mg/dL}$ at baseline will be summarized as a continuous variable. If CRP had not normalized at the timepoint assessed (i.e 8 week visit date (for SSA) or 26 weeks visit date for the final analysis), the patients concerned will not be included in the analysis for this outcome.
- CRP change from baseline at 26 weeks (%) will be summarized as a continuous variable.

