10 TABLES, FIGURES AND LISTINGS

10.1 List of tables

Table 1 – Protocol deviations summary overview

Table 2 – Demographics

Table 3 – Pericarditis History

Table 4 – Cardiovascular History

Table 5 – Other medical history by MedDRA System Organ Class

Table 6 – Other medical history by MedDRA Preferred Term

Table 7 – Baseline medication by WHO Anatomical Therapeutic Chemical (ATC) Classification

Table 8 – Anthropometric assessment and vital signs at baseline – Descriptive statistics

Table 9 – Physical examination at baseline – Descriptive statistics

Table 10 –Questionnaire at baseline: NRS and C-SSRS – Descriptive statistics

Table 11 – Standard 12-lead Electrocardiogram (ECG) at baseline – Descriptive statistics

Table 12 –Laboratory tests results at baseline – Descriptive statistics

Table 13 –Laboratory tests results at baseline – Descriptive statistics by gender

Table 14 –Laboratory tests results at baseline below, within and above the normal range

Table 15 – Study drug exposure

Primary efficacy endpoint

Table 16 – Primary endpoint – Worst 11-point NRS score at Week 8 and 11-point NRS change from baseline to Week 8 – Descriptive statistics

Additional efficacy endpoints

Table 17 – Worst 11-point NRS score and change from baseline by week up to 26 weeks – Descriptive statistics

Table 18 – Patients with normalized CRP levels (i.e with a CRP \leq 0.5 mg/dL) at 8 weeks and 26 weeks (for patients with CRP \geq 1.0 mg/dL at baseline)

Table 19 – Time to CRP normalization (in weeks) for patients with CRP \geq 1.0 mg/dL at baseline

Table 20 – CRP change from baseline at 26 weeks – Descriptive statistics

Table 21 – Patients with pericarditis recurrence during the extension period (EP),

Further exploratory endpoints

Table 22 – Worst 11-point NRS score and change from baseline by week up to 26 weeks for patients enrolled with qualifying CRP ≥ 1.0 mg/dL – Descriptive statistics

Table 23 – Worst 11-point NRS score and change from baseline by week up to 26 weeks for patients for patients who qualified for the trial on basis of past CMR findings and had qualifying CRP < 1.0 mg/dL – Descriptive statistics

Safety related

Table 24 – Overview of reported adverse events

Table 25 – Non-serious adverse events by MedDRA System Organ Class

Table 26 – Non-serious adverse events by MedDRA Preferred Term

Table 27 – Serious adverse events by MedDRA System Organ Class

Table 28 – Serious adverse events by MedDRA Preferred Term

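### Percent CRP change at Week 26 is not limited to baseline CRP ≥1.0 mg/dL, so patients who entered on CMR with lower CRP can dilute its mean

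*SAP*

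**What the plan says.** Protocol 4.1.3 and SAP 2.3.2 list four CRP endpoints, and SAP 8.5.2 gives their analysis. Three concern normalization: "Percentage of patients with normalized CRP levels at 8 weeks (for patients with CRP", "Percentage of patients with normalized CRP levels at 26 weeks (for patients with CRP" and "Time to CRP normalization for patients with CRP". Each goes on to give the 1.0 mg/dL baseline cut-off. The fourth is "CRP change from baseline at 26 weeks", expressed as a percentage, and it has no cut-off. SAP 8.5.2 keeps it that way: "CRP change from baseline at 26 weeks (%) will be summarized as a continuous variable".

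The table list follows the same pattern. Tables 18 and 19 name the cut-off. The entry "Table 20 – CRP change from baseline at 26 weeks – Descriptive statistics" does not, and it also drops the percent sign.

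Inclusion criterion 4 accepts CMR evidence of inflammation as an alternative to raised CRP. SAP 8.3.2 sets up a category for these patients, "Pericarditis confirmed by CMR only (CRP < 1.0 mg/dL". SAP 8.5 places all scheduled-visit data in the descriptive summaries, and nothing removes these patients from Table 20.

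Other SAP provisions bear on the point:
- Section 7 lists a second unrestricted summary under additional efficacy endpoints: "CRP change from baseline at 8 weeks will be summarized as a continuous variable".
- Section 7 also plans a CRP change by visit for patients with baseline CRP of at least 1 mg/dL, not stated as a percentage.
- Section 9.1 asks for the median, IQR, minimum and maximum beside the mean and SD.
- Section 8.3.10 codes results reported as below a limit as 0, with CRP <0.3 mg/dL as its example.

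**The concern.** Two different groups are pooled on a scale that suits only one of them. In a patient with raised CRP, percent change measures how far the inflammation marker has fallen. In a patient who entered on CMR with CRP below 1.0 mg/dL there is less to lower, and a rise of a few tenths of a mg/dL can be a large percentage. A fall cannot exceed 100%, while a rise has no bound, so the arithmetic mean leans upward.

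The trial has no control arm and plans no inference, so the descriptive summaries are the whole of the efficacy evidence. Protocol 3.5 says the results will inform the feasibility of a randomized withdrawal trial. A mean CRP change that moves with the proportion of patients entering by each route is hard to read as an effect of treatment.

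**Working it through.** The plan states no expected CRP change and no sample size calculation, so there is no figure to reproduce. What follows is illustration.

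**Inputs.** From the documents: about 25 patients (Protocol 5.1 and 11.1), entry by CRP or by CMR (Protocol 5.2), and no cut-off for the percent change (SAP 8.5.2). Assumed, because the documents are silent:
- the number k of CMR-only patients is 0, 5, 10 or 15
- patients with CRP ≥1.0 mg/dL have a geometric mean ratio (Week 26/baseline) of 0.20
- CMR-only patients have a ratio of 1.00
- the log ratio is normal with SD s = 0.8 in both groups.

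**Expected mean percent change in each group.** For a log-normal ratio with geometric mean g, this is 100 × (g × exp(s²/2) − 1). With s = 0.8, exp(0.32) = 1.377.
- CRP ≥1.0: 100 × (0.20 × 1.377 − 1) = -72.5%
- CMR-only: 100 × (1.00 × 1.377 − 1) = +37.7%, although the typical patient does not change.

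**Pooled mean.** [(25 − k) × (-72.5) + k × 37.7] / 25. For k = 10: (15 × (-72.5) + 10 × 37.7) / 25 = -28.4%.

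**Pooled geometric change.** 100 × (0.20^((25 − k)/25) − 1). For k = 10: 0.20^0.6 = 0.381, so -61.9%.

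The median and the chance of a positive value come from simulated trials with fixed group sizes.

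| CMR-only of 25 | Mean | Geometric | Median | Trials with mean > 0 | Trials with median > 0 |
|---|---|---|---|---|---|
| 0 | -72.5% | -80.0% | -80% | 0% | 0% |
| 5 | -50.4% | -72.4% | -74% | 0.4% | 0% |
| 10 | -28.4% | -61.9% | -63% | 6% | 0% |
| 15 | -6.4% | -47.5% | -42% | 33% | 0.7% |

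With 10 CMR-only patients the mean moves 44 points and the geometric change 18. Some of the shift is therefore plain population mix, and the rest comes from averaging on the percent scale.

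**Sensitivity to s.** The same formula with s = 0.6 (exp(0.18) = 1.197) gives means of -76.1%, -56.9%, -37.7% and -18.6% for k = 0, 5, 10 and 15. With s = 1.0 (exp(0.5) = 1.649) it gives -67.0%, -40.6%, -14.3% and +12.1%.

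**Fixed-value check.** Give every raised-CRP patient a 90% fall, and let c be the common percent change in CMR-only patients. The mean is [(25 − k) × (-90) + k × c] / 25.
- c = +200% (0.1 to 0.3 mg/dL): -32.0% at k = 5 and +2.8% at k = 8, where the sign turns.
- c = 0: -72.0% at k = 5.
- c = -50%: -82.0% at k = 5, with no reversal at any k.
- A single CMR-only patient would need a rise of 24 × 90 = 2160% to bring the mean to zero.

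**Zero baselines.** A baseline of <0.3 mg/dL is coded 0 under SAP 8.3.10, so its percent change divides by zero. The SAP has no rule for this case.

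**The case against.** The strongest reply is that the SAP does not rely on the mean. Section 9.1 requires the median, IQR and range, and Protocol 11.2 chooses between mean and median according to the distribution. Tables 18 and 19 report CRP response in the raised-CRP group beside Table 20, and section 7 has a restricted change by visit. The endpoint is one of six additional descriptive ones in a pilot, and the SAP follows the protocol's definition faithfully.

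Much of this stands. The median resists distortion far better, and a reader with all the tables would be unlikely to infer that there was no effect. But the median still moves, from -80% to -63% with 10 CMR-only patients in the assumed case, and the SAP does not say which statistic leads. The restricted summary in section 7 belongs to the staged analysis, is not stated as a percentage and has no matching entry in the table list. Part of section 7 is missing from the text available here, so its full scope cannot be judged.

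It is also fair to object that the log-normal illustration does not test small denominators. Percent change depends only on the ratio, and both groups were given the same spread, so the baseline level plays no part. The illustration shows the effect of mixing groups on this scale and nothing more.

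A reader might infer that CMR-only patients will drive or reverse the average. The documents do not support that: the count and CRP values are unstated, and if those patients fall as much as the rest there is no distortion. Nor does CMR-only mean normal CRP. The category is below 1.0 mg/dL, whereas SAP 8.5.2 sets normalization at 0.5 mg/dL or less.

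**Conclusion.** The gap is real and follows from the text. Among the listed CRP endpoints, only the Week 26 percent change lacks the 1.0 mg/dL cut-off. That statement covers the listed endpoints, not every CRP summary in the SAP, since the Week 8 change in section 7 is unrestricted too.

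The usual consequence is dilution. In the assumed case the mean weakens from -72% to -50%, -28% and -6% with 5, 10 and 15 CMR-only patients. Reversal is less likely: 0.4%, 6% and 33% of simulated trials at those counts. These sizes rest wholly on the assumed fall, the absence of change in CMR-only patients, the spread and k. More spread makes reversal likelier and less spread makes it rarer. The point is worth correcting because the correction is simple, but it does not affect the primary endpoint or any test.

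**What to change.** Present Table 20, and the Week 8 CRP change in SAP section 7, separately for baseline CRP ≥1.0 and <1.0 mg/dL. Use the at-baseline definition of Tables 18 and 19. Tables 22 and 23 use qualifying CRP, which section 7 treats as a separate variable.

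- In the ≥1.0 group, lead with the median and IQR of percent change, with the mean and SD beside them.
- In the <1.0 group, report absolute change in mg/dL. This also avoids the undefined percent change when the baseline is coded 0.
- Report a geometric mean ratio only if values below the limit are given a non-zero value for that calculation, for example the limit or half of it. Under the present rule, a patient whose CRP falls below the limit would have a ratio of zero and no logarithm.
- State in the Table 20 title that the change is a percentage, and give the rule for a zero baseline.

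The cost is a few lines of SAP text and one split of existing data, with no new data collection. The drawback is that the leading estimate rests on fewer patients than the full set.

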8.5.3 Further exploratory analyses

- Evaluate the NRS for patients with qualifying $CRP \geq 1.0 \text{ mg/dL}$
- Evaluate the NRS for patients who qualified for the trial on basis of past CMR findings and had qualifying $CRP < 1.0 \text{ mg/dL}$
- Examine the correlation between medications used to treat pericarditis and the NRS score at different time points.
- Perform a numerical comparison with the historical data from the rilonacept phase 2 and RHAPSODY trials for the patients with similar eligibility criteria. The methodology to do this analysis will be addressed in a separate SAP.

8.6 Safety analysis

The Safety analysis set will be used for all safety analysis.

8.6.1 Adverse events (AEs)

The number of adverse events and percentage of patients with at least one adverse event will be summarized by system organ class and by preferred terms (MedDRA).

AEs will be considered as treatment - emergent adverse events (TEAE) if the event onset time (and date) is $>$ start of the IMP. Adverse events with incomplete onset dates will be summarized as TEAE regardless of severity and relationship to the IMP.

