## 9 CONDUCT OF THE STUDY

### 9.1 *Scheduling of Study Procedures*

Patients diagnosed with recurrent pericarditis will be invited to participate in the study. Informed consent must be obtained PRIOR to performing any study-related procedure. There is no time limit between obtaining informed consent and assigning study treatment to the patient. Some of the scheduled follow-up visits may be performed remotely if it's not possible to conduct an in-patient visit. The following must be in place to enable a remote visit to take place:

- The patient is able to obtain an ECG recording, which can immediately be transmitted to the study site
- The patient agrees to go to a local laboratory to have the blood tests planned by protocol performed

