2.3.4 Safety endpoints

Per section 4.2.2 of the study protocol (Amendment #2), the safety outcomes will encompass the following:

- Occurrence of adverse / serious adverse events as of the start of the IMP through the last study visit.

- Change (from baseline) in C-SSRS at the end of patient follow-up – i.e. either at week 8 or week 26-week study visit.
- Change (from baseline) in laboratory parameters, including liver function parameters and INR at the end of patient follow-up – i.e. either at the week 8 or the week 26 study visit.
- Change (from baseline) in ECG intervals/findings parameters at the end of patient follow-up – i.e. either at the week 8 or the week 26-week study visit.

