9.5 Imputation of Dates

9.5.1 Adverse events

If year is present and month and day are missing (e.g XX-XXX-2020)

- If year = year of first dose, then set month and day to month and day of first dose unless end date is before date of first dose, in which case the onset date is set to 28 days prior to end date.
- If year < year of first dose, then set month and day to December 31st.
- If year > year of first dose, then set month and day to January 1st.

If month and year are present and day is missing (e.g XX-Jun-2022)

- If year = year of first dose and if month = month of first dose then set day to day of first dose date unless end date is before date of first dose, in which case the onset date is set to 28 days prior to end date.
- if month < month of first dose then set day to last day of month
- if month > month of first dose then set day to 1st day of month
- if year < year of first dose then set day to last day of month
- if year > year of first dose then set day to 1st day of month

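### SAP 8.6.1 labels every adverse event with an incomplete onset date treatment-emergent, including events that SAP 9.5.1 dates before the first dose

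*SAP*

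**What the plan says.** SAP 8.6.1 has two rules for treatment-emergent status. An event qualifies "if the event onset time (and date) is $>$ start of the IMP". For partial dates it adds: "Adverse events with incomplete onset dates will be summarized as TEAE regardless of severity and relationship to the IMP".

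SAP 9.5.1 imputes partial AE onset dates relative to the first dose, and several of its rules place the onset before dosing:

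- Year only, earlier than the first-dose year: "If year < year of first dose, then set month and day to December 31st".
- Month and year known, earlier month of the same year: "if month < month of first dose then set day to last day of month".
- Month and year known, earlier year: "if year < year of first dose then set day to last day of month".
- Same year, or same month and year, as the first dose: the first-dose date is used, "unless end date is before date of first dose, in which case the onset date is set to 28 days prior to end date".

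SAP 2.3.4 defines the safety endpoint as "Occurrence of adverse / serious adverse events as of the start of the IMP through the last study visit". No sentence says whether 8.6.1 or 9.5.1 decides TEAE status when they disagree.

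The titles of Tables 24 to 28 in SAP 10.1 do not mention treatment emergence. Protocol 9.1 (Visit 1) starts AE recording at consent, so pre-dose events can be in the database.

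**The concern.** Counting an event as treatment-emergent when its onset cannot be placed relative to dosing is a usual and sensible default. The 8.6.1 sentence goes further. It applies the default where the recorded year, month or end date already shows that the event began, or even finished, before the first dose. For those events the 9.5.1 imputation has no role in TEAE status, and two programmers who each follow one section would flag the same event differently.

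The pilot's stated purposes include tolerance and safety (Protocol 3.5), and its safety results are descriptive counts in about 25 patients. Pre-dose events in an on-treatment count would inflate that count and depart from the window set in 2.3.4.

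**Working it through.** The documents give no figure to reproduce, so the check runs the 9.5.1 rules against 8.6.1.

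**Inputs.** The imputation rules are those of SAP 9.5.1 and the TEAE rules those of SAP 8.6.1. The sample size is about 25 (Protocol 11.1). For illustration I assume a first dose on 15 Mar 2023 and, where the pattern needs an event that ended before dosing, an end date of 14 Mar 2023.

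| Known part of onset date | Onset after 9.5.1 | Relative to first dose | 8.6.1 |
|---|---|---|---|
| Year, same; no early end | 15 Mar 2023 | same date | TEAE |
| Year, same; ended before dose | 14 Feb 2023 | before | TEAE |
| Year, earlier | 31 Dec 2022 | before | TEAE |
| Year, later | 1 Jan 2024 | after | TEAE |
| Month and year, same; no early end | 15 Mar 2023 | same date | TEAE |
| Month and year, same; ended before dose | 14 Feb 2023 | before | TEAE |
| Month, earlier in same year (Feb 2023) | 28 Feb 2023 | before | TEAE |
| Month, later in same year (Apr 2023) | 1 Apr 2023 | after | TEAE |
| Month and year, earlier year (Dec 2022) | 31 Dec 2022 | before | TEAE |
| Month and year, later year (Jan 2024) | 1 Jan 2024 | after | TEAE |

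**Count.** 9.5.1 gives 5 before, 2 on the first-dose date and 3 after. 8.6.1 labels all 10 TEAE, so the two sections disagree on 5 of 10 patterns. These are patterns of date, not expected frequencies of events.

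**After the correction.** If status follows the imputed date, and an imputed date equal to the first-dose date counts as TEAE, then 2 + 3 = 5 patterns are TEAE and 5 are not.

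**How often it can arise.** Protocol 9.1 lists consent among the Visit 1 procedures, within 72 hours of Day 1, and SAP 4.3 places the first dose on the evening of the screening visit. AEs count only from consent, so the scheduled pre-dose window is hours to three days. Within it, the three patterns with an earlier year or month need consent and first dose to straddle a month or year boundary. The other two need an event that started and ended inside the window. An example on schedule: consent 30 Jan, onset recorded only as January, first dose 1 Feb. 9.5.1 gives 31 Jan, before the dose; 8.6.1 gives TEAE.

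**Size.** One patient is 1/25 = 4 percentage points of the proportion with at least one TEAE, if that patient has no other TEAE. The number of partial dates is not in the documents. Over an assumed range of 1 to 3 such patients the inflation is 1/25 = 4 to 3/25 = 12 points.

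**The case against.** The strongest case on the other side is that little turns on this. The study is a single-arm descriptive pilot, the rule errs towards over-counting, all AEs appear in Listing 5, and SAP 6 provides for a data review before database lock. That stands as a limit on size. It does not remove the contradiction.

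Four stronger readings are tempting, and the documents do not support them.

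- *Pre-dose events are attributed to the drug.* TEAE is a label of timing. Relationship to study drug is recorded separately (Protocol 9.2.11.1).
- *The strict inequality loses reactions to the first dose.* Cases that 9.5.1 imputes to the first-dose date have incomplete dates, so the 8.6.1 sentence already makes them TEAEs. Day 1 events with a clock time are sorted correctly. Only a Day 1 event with a full date and no time is left unclear, and it may be read as incomplete and hence a TEAE.
- *The pre-dose window is long.* Protocol 9.1 does say: "There is no time limit between obtaining informed consent and assigning study treatment to the patient". The Visit 1 schedule in the same section and SAP 4.3 make a gap of weeks an edge case. An onset known only as December 2022 with a first dose on 25 Jan 2023 would need consent at least 25 days before dosing (31 Dec to 25 Jan).
- *The AE tables will show wrong counts.* No title in Tables 24 to 28 mentions TEAE. If those tables hold all recorded AEs, the flag changes none of their counts.

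**Conclusion.** The contradiction is real in the current SAP. Read literally, 8.6.1 classifies as treatment-emergent some events that the SAP's own date rules place before dosing, contrary to 9.5.1 and to the window in 2.3.4. The direction is over-counting of on-treatment events.

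The effect is probably small. The 4-point figure per patient rests on about 25 patients, on that patient having no other event in the same row, and on the table being restricted to TEAEs, which the SAP does not state. The actual number of affected events cannot be known from the documents.

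A reader might conclude that the blanket sentence should simply be deleted. It should not be: 9.5.1 has no rule for a wholly missing onset date, so that sentence is the only one covering such events, and removing it would leave them unclassified.

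**What to change.** Replace the partial-date sentence in SAP 8.6.1 with a derivation along these lines:

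- TEAE status is derived from the onset date after imputation by 9.5.1. Onset on or after the first dose is a TEAE, using the clock time where it is recorded.
- If onset is on the first-dose date and the time is missing, the event is a TEAE.
- If the onset date is wholly missing, or otherwise cannot be placed relative to the first dose, the event is a TEAE unless its end date is before the first dose.
- An event whose known date parts or end date show onset before the first dose is not a TEAE.

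In SAP 10, state which of Tables 24 to 28 are restricted to TEAEs, and flag pre-dose AEs in Listing 5 so that they stay visible.

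The cost is a few sentences, one derivation and one flag. No data collection changes. A few events may move into or out of the TEAE counts.
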